5.0 SAMPLE SIZE

Sample size calculations for hierarchical regression models are difficult, as they require estimates of the number of clusters, the size of each cluster, the effect of intervention on each cluster separately and intra-cluster correlation. Without prior information, these estimates are unlikely to be accurate. Hence, statistical power and sample size calculations will be based on practical considerations.

It is hypothesized that if the use of PREDICT 2.1 decreases the odds of Oncotype DX ordering by approximately 50% or more, the usage of Predict 2.1 will be of clinical importance. It is known that approximately 300 patients are seen in a given six-month period in Ottawa, and approximately 15% of eligible patients undergo Oncotype DX testing. For the other centres, the values are 75 and 75% (Newmarket), 75 and 90% (Windsor), 75 and 65% (Kingston), 35 and 65% (Thunder Bay), and 75 and 90% (Grand River). Based on these estimates,

a simple, two-sided, $\alpha=0.05$, logistic regression model would have 80% power to detect an odds ratio of 0.46 (from 15% to 7.46%) in Ottawa, an odds ratio of 0.38 (from 90% to 77.4%) in Grand River/Windsor, and an odds ratio of 0.53 (from 70% to 55.4%) in Newmarket/Kingston/Thunder Bay. Overall, if one conservatively estimates at least 500 patients will be eligible pre-intervention and 500 patients will be eligible post-intervention, a simple logistic regression analysis would have over 80% power (2-sided, $\alpha=0.05$) to detect an odds ratio of 0.67, assuming that approximately 50% of patients undergo Oncotype DX testing in the pre-intervention period. Combined, these estimates give assurance that the sample size for this study is sufficient to capture clinically meaningful effects.

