3.0 METHODS

3.1 Study Design

A multi-center prospective cohort study, with a pre- versus post-comparison, evaluating how making PREDICT 2.1 results available to treating physicians impacts on subsequent ordering of Oncotype DX ®, chemotherapy use, time to commencement of chemotherapy, and health care resource utilization. In addition, in order to understand physician reasoning and comfort with making systemic therapy decisions with either PREDICT 2.1, Oncotype DX ® or both, a physician questionnaire will be performed in order to drive subsequent knowledge mobilisation strategies.

The study will involve participation from 6-8 Ontario sites that will be chosen to reflect a diverse patient population in Ontario and the site's involvement in the REaCT program.

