4.0 STATISTICAL ANALYSIS

The primary analysis will be based on a hierarchical logistic regression analysis, with time period (pre-intervention versus post-intervention) as the primary covariate of interest. For this model, patient characteristics are considered nested within treating physician, which is nested within treatment centre. Adjustments will be performed for baseline characteristics. From our survey, it was evident that there was significant variability between centres (and between physicians) for ordering Oncotype DX. Data from Ottawa shows that approximately 15% of approximately 600 patients treated by 8 physicians have this test performed. In contrast, Kingston (5 physicians) sees around 200 eligible patients a year and Oncotype DX is ordered for around 65% of these patients,

Thunder Bay (3 physicians) sees around 70 patients a year and also tests around 65% of eligible patients, and Newmarket (3 physicians) sees around 130 eligible patients a year and Oncotype DX is ordered for around 75% of these patients. Windsor (3 physicians) and Kitchener (4 physicians) both see around 150 patients per year and orders Oncotype DX testing on 90% of eligible patients. Given concerns that use of hierarchical clusters may not sufficiently account for the substantial variability between sites, analyses will also be conducted by site, grouped by baseline rate of testing (i.e. Kingston, Thunder Bay and Newmarket will be combined, as will Windsor and Kitchener; Ottawa will be a separate group on its own). A similar analysis will be performed using hierarchical logistic regression. In addition, key supportive analyses will also be performed using a two-sample chi-square test within each site separately, comparing the change in proportion of patients for which Oncotype DX is ordered for each physician (i.e. post-intervention proportion – pre-intervention proportion for physician A, B, C, ...).

Analyses of secondary endpoints will be performed globally across all sites combined, and for each site individually. The chi-square test or Wilcoxon rank sum test will be used as appropriate for categorical or continuous endpoints respectively. Results will be presented using tables and figures, and exact confidence intervals will be constructed for outcomes of interest. Bootstrapping may be used for estimation purposes if required. All tests will be two-sided and statistical significance will be defined at the $\alpha=0.05$ level.

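### Does the stated power of over 80% for an odds ratio of 0.67 mislead because the primary model is hierarchical and the centres range from 15% to 90%?

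*Combined protocol and SAP*

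**What the plan says.** Section 4.0 sets the analysis: "The primary analysis will be based on a hierarchical logistic regression analysis", with patients nested in physicians and physicians in centres. It reports that "there was significant variability between centres (and between physicians) for ordering Oncotype DX".

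Section 5.0 explains that sizing such a model needs cluster inputs that are not reliably known, and that it will take a simpler, practical route. Its target is an intervention that "decreases the odds of Oncotype DX ordering by approximately 50% or more". It gives detectable odds ratios for three groups of centres with similar baseline rates: 0.46 for Ottawa, 0.38 for Grand River and Windsor, and 0.53 for Newmarket, Kingston and Thunder Bay. It then gives one overall figure. It starts from "Overall, if one conservatively estimates at least 500 patients will be eligible pre-intervention" and the same number afterwards, and says that "a simple logistic regression analysis would have over 80% power" "to detect an odds ratio of 0.67, assuming that approximately 50% of patients undergo Oncotype DX testing in the pre-intervention period". Its conclusion that the sample size suffices rests on all these figures together.

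**The concern.** The 50% baseline is an average that no listed centre resembles. A binary outcome carries most information about a log odds ratio near 50%, and less near 15% or 90%. The primary model compares periods within centres and physicians, so it works with the information at the actual centre rates. No power is given for that model.

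A reader could set 0.67 beside the target of 0.50 and beside the odds ratio that the primary model will report. That reader would conclude that the study can reliably detect effects much weaker than its target. If that were what the plan claimed, its only overall power figure would be too favourable, and a null result would be read as stronger evidence against a modest effect than it is.

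**Working it through.** **Inputs.** Two-sided alpha 0.05 (section 4.0). Six-month volumes and baseline rates (section 5.0): Ottawa 300 at 15%, Newmarket 75 at 75%, Windsor 75 at 90%, Kingston 75 at 65%, Thunder Bay 35 at 65%, Grand River 75 at 90%. The total is 635 per period. The mean rate is (45 + 56.25 + 67.5 + 48.75 + 22.75 + 67.5)/635 = 307.75/635 = 48.5%. Mean within-centre p(1−p) is 0.143, against 0.25 at a uniform 50%.

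**1. The plan's own figure.** From p1 = 0.50, an odds ratio of 0.67 gives p2 = 0.67/1.67 = 0.401. With 500 per period, SE(log OR) = √[1/(500×0.25) + 1/(500×0.401×0.599)] = 0.1278. Then |ln 0.67|/SE = 0.4005/0.1278 = 3.134, and power = Φ(3.134 − 1.960) = 88.0% (88.2% with the pooled-variance test of two proportions). Over 80% is correct. This model's 80%-detectable odds ratio is 0.70.

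**2. Centre-adjusted model with 0.67 as a common within-centre odds ratio.** For each centre let a = n·p1(1−p1) and b = n·p2(1−p2). The information is Σ ab/(a+b), and SE is the inverse of its square root. Physician variation is set to zero. At 500 per period (each volume × 500/635):

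| Centre | n | p1 | p2 | a | b | ab/(a+b) |
|---|---|---|---|---|---|---|
| Ottawa | 236.2 | 0.15 | 0.106 | 30.12 | 22.34 | 12.83 |
| Newmarket | 59.1 | 0.75 | 0.668 | 11.07 | 13.10 | 6.00 |
| Windsor | 59.1 | 0.90 | 0.858 | 5.31 | 7.21 | 3.06 |
| Kingston | 59.1 | 0.65 | 0.554 | 13.44 | 14.59 | 6.99 |
| Thunder Bay | 27.6 | 0.65 | 0.554 | 6.27 | 6.81 | 3.26 |
| Grand River | 59.1 | 0.90 | 0.858 | 5.31 | 7.21 | 3.06 |

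The sum is 35.20, SE = 0.1685, and power = Φ(0.4005/0.1685 − 1.960) = Φ(0.416) = 66.1%. Repeating this:

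| Per period | Power at 0.67 | 80%-detectable OR | Power at 0.50 |
|---|---|---|---|
| 500 | 66.1% | 0.62 | 98.2% |
| 635 (section 5.0 volumes) | 76.4% | 0.66 | 99.5% |
| 650 (half of section 4.0's annual 1,300) | 78.1% | 0.66 | 99.7% |

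Simulation (20,000 trials, logistic regression with centre effects) gave 66.8% and 76.7% at 0.67 for 500 and 635.

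**3. Put both figures on one scale.** A within-centre odds ratio of 0.50 takes the rates to 8.1% (Ottawa), 60.0% (Newmarket), 81.8% (Windsor, Grand River) and 48.1% (Kingston, Thunder Bay). The overall rate moves from 48.5% to 38.6%. The pooled odds ratio is (0.386/0.614)/(0.485/0.515) = 0.668. Solving the other way, a pooled 0.67 is a within-centre 0.502. A within-centre 0.67 is only about 0.79 pooled (48.5% to 42.7%).

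For the same shift in ordering, therefore, the simple formula at 500 per period gives about 88% and the centre-adjusted model about 98%.

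**4. Physician variation (not given in the documents, so assumed).** The three-level model's odds ratio is also conditional on physician, so the figures in step 2 are its favourable end. With a physician intercept SD of 1.0 on the logit scale, the 80%-detectable odds ratios are about 0.60 (500) and 0.64 (635), and power at 0.50 is about 96% and 99%. In the least favourable case tried (intercept SD 1.0, period effect varying between physicians with SD 0.5, 500 per period), power at 0.67 is about 47% and at 0.50 about 90%. Section 4.0 specifies no random period effect, so that case goes beyond the stated model.

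**5. Number of sites.** "The study will involve participation from 6-8 Ontario sites", but only six are listed. If each added site saw 75 patients per period at a rate between 15% and 90% (assumption), full-volume power at a within-centre 0.67 would be about 80–83% with seven sites and 83–89% with eight, before physician variation.

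**The case for a change.** The strongest case for a change is that correcting for centre needs none of the unknown inputs the plan cites: section 5.0 already lists each centre's volume and rate. Section 5.0 also puts odds ratios for groups of similar centres next to an overall one without comparing the scales. A label on 0.67 and one sentence with the centre-adjusted figures would cost nothing and would help in reading a result weaker than 0.50.

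The arithmetic behind this stands: 0.67 must not be carried over to the primary model's scale. What does not stand is that the plan carries it over. A single logistic regression on all patients with one overall baseline can only yield a pooled odds ratio, and the plan says it is using a simplification. Nor does it ignore centre differences. Its three group figures are close to the within-centre scale and slightly cautious: the pooled-variance test gives about 83–84% power for each, against the stated 80%. Two of them, 0.46 and 0.38, show openly that single groups need an effect stronger than 0.50.

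The proposed sentence would also bring its own difficulty. The range 0.62 to 0.66 belongs to a centre-only model with no physician variation, and giving it as the power of the three-level model would overstate what is known.

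**Conclusion.** The concern does not hold as a fault in the plan. The overall statement is true for the model it names (about 88% power at 0.67). At the listed sites it describes nearly the same alternative as the plan's target of halving the odds. For that alternative the centre-adjusted model has about 98% power at 500 per period and over 99% at 635, so before physician variation the stated figure is conservative. Under the assumed physician variation, power at 0.50 stays at about 90% or more in every scenario tried.

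The figure looks too favourable only if 0.67 is moved to a scale the plan did not use, where power is about 66% to 76% with six sites. Using the simple model was a fair and disclosed trade-off. A label or an added sentence would alter neither the sample size, nor the analysis, nor the conclusion of section 5.0. These results rest on the listed volumes and rates and, in steps 2 and 3, on a common effect across centres.

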6.0 STUDY TIMELINE

Funding to begin: Sept 1, 2019

Application to OCREF Sept 2019

REB approval Nov 2019

Site initiation visits Dec 2019-Feb 2020

Completion of initial 6-months of study May 2020

Educational intervention June 2020

Completion of second 6-months of study December 2020

Data analysis Jan-Feb 2021

Funding term end date: March 31, 2021

Table 1. Characteristics of study algorithms

Algorithm name	Required clinic-path data	Formula	Population – LN pos and neg?	What it tells you
NHS Predict 2.1	Age Screen detected or not Tumour size LN involvement Grade ER Her2 Ki67*	On line	Node pos Node neg	10 yr distance disease free survival
Magee 1	Tumour size Grade, ER PR Her2 Ki-67	On line	Macro-node negative	Surrogate Oncotype score
Magee 2	Tumour size, grade, ER, PR, Her2 without Ki-67	On line	Macro-node negative	Surrogate Oncotype score
Magee 3	ER, PR, HER2 Ki-67	On line	Macro-node negative	Surrogate Oncotype score
Gage et al (2015)	ER PR Grade simple algorithm based on tumor grade, PR >1% and ER>20%.			
University of Tennessee predictive algorithm	PR Grade			Surrogate Oncotype score

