3.3 Study Procedures

Each site will have a different process for determining eligibility. Research staff at each site will be confirming Oncotype DX ® eligibility from pathology reports and will be working with New Patient booking staff (or similar) to get weekly/daily clinic lists of new patients whose tumors meet eligibly for Oncotype DX ® testing.

Patient tumours at each site will enter study screening when a complete pathology report is received. Once a patient tumour is deemed eligible, it is given a Study ID number. Pathology data is collected by study staff. At all points of the study, patients with eligible tumours will meet with their treating physician to discuss the individualised testing and treatment plan that is best for them.

Once the physician meets with the patient, we will also collect the chemotherapy treatment plan details.

After 3 months of activation, physicians will start completing a questionnaire for each new patient with an eligible tumour. Delaying the questionnaires for the first 3 months is to prevent bias.

After 6 months of activation, the physicians will receive a teaching session (Intervention) consisting of PowerPoint slides which will present an updated review on the benefits and limitations of Oncotype DX and PREDICT testing.

After this teaching session, study staff at each site will be using the pathology data to run the PREDICT tool for each patient and will provide the results to each physician prior to his/her meeting with each patient. Again after 3 months, we will re-introduce the physician questionnaire for the last 3 months of the study.

In summary:

Month 1 to 3: pathology and chemo data collected, NO physician questionnaire

Month 4 to 6: pathology and chemo data collected, PLUS physician questionnaire

Intervention teaching after 6 months of study activation

Month 7 to 9: pathology and chemo data collected, PREDICT 2.1 tool used, NO physician questionnaire

Month 10 to 12: pathology and chemo data collected, PREDICT 2.1 tool used, PLUS physician questionnaire

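### Section 6.0 dates do not fit the per-site clock, and with no data cut or common window, shorter post-period chart follow-up can mimic less chemotherapy and slightly faster starts (secondary endpoints only)

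*Combined protocol and SAP*

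**What the plan says.** Section 6.0 (Study Timeline) lists "Site initiation visits Dec 2019-Feb 2020", then single dates for the whole study: "Completion of initial 6-months of study May 2020", "Educational intervention June 2020", "Completion of second 6-months of study December 2020" and "Data analysis Jan-Feb 2021". The last entry is "Funding term end date: March 31, 2021".

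Section 3.3 (Study Procedures) counts from activation: "After 3 months of activation, physicians will start completing a questionnaire for each new patient with an eligible tumour", and "After 6 months of activation, the physicians will receive a teaching session (Intervention". Section 3.4 (Study Schedule) adds that every site has its own start date and its own pre and post periods.

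Section 3.8 (Data Collection) says when collection starts for a patient (a complete, eligible pathology report). It lists the planned regimen, the chemotherapy received, and the time from the medical-oncology visit to chemotherapy start. It does not say when collection ends. Section 3.7 also compares health system costs before and after, with chemotherapy as a component. Section 4.0 assigns chi-square or Wilcoxon rank sum tests to the secondary endpoints. It has no rule for a patient whose treatment has not started when the chart is read.

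**The concern.** There are two linked problems. First, the calendar in section 6.0 cannot be met by most sites on the clock in sections 3.3 and 3.4, and the analysis slot overlaps accrual at late sites. Second, nothing fixes how long after the visit a chart is followed. At one common cut, nearly every pre-period chemotherapy start would be on file, while the most recent post-period starts would not.

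This pushes results in a predictable direction after PREDICT becomes available: less chemotherapy received, shorter times among those seen to start, and lower chemotherapy cost. All three bear on stated secondary aims, and the cost result is to be extrapolated to Ontario. A reader could take the artefact for an effect of the intervention.

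**Working it through.** **1. The plan's dates.** Add 6 and 12 months to activation, taking activation as no earlier than the initiation visit (the documents give no activation dates).

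| Site active | 6 months | 12 months | Weeks to 28 Feb 2021 | Weeks to 31 Mar 2021 |
|---|---|---|---|---|
| 1 Dec 2019 | 1 Jun 2020 | 1 Dec 2020 | 12.7 | 17.1 |
| 1 Jan 2020 | 1 Jul 2020 | 1 Jan 2021 | 8.3 | 12.7 |
| 1 Feb 2020 | 1 Aug 2020 | 1 Feb 2021 | 3.9 | 8.3 |
| 29 Feb 2020 | 29 Aug 2020 | 28 Feb 2021 | 0 | 4.4 |

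The first row reproduces section 6.0. The January and February rows miss the May close and the June teaching date, and February sites are still accruing during the analysis slot. Activation later than the initiation visit would widen the gap.

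**2. Follow-up difference.** Patients entering at the same point of each period at one site enter at activation + x and activation + 6 months + x. At any common cut the second has six months less chart time. This needs no assumption about lags.

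**3. Starts not seen.** The documents give no lag from entry to chemotherapy start, so the following is assumed: gamma lag (shape 4) with mean 6, 8 or 10 weeks, and uniform entry over 26 weeks. With g weeks from last entry to the cut, and S(u) the probability that the lag exceeds u:

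unseen(g) = (1/26) × integral of S(u) from g to g + 26

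| g (weeks) | mean 6 | mean 8 | mean 10 |
|---|---|---|---|
| 4 | 8.9% | 16.0% | 23.4% |
| 8 | 2.1% | 6.0% | 11.5% |
| 12 | 0.3% | 1.8% | 4.7% |

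For pre-period patients g is 26 weeks longer and the unseen share is 0.03% or less.

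**4. Effect on the proportion treated.** Observed rate = true rate × (1 - unseen). With an assumed true rate of 25% in both periods, the post-period rate reads 25 × (1 - 0.089) = 22.8% to 25 × (1 - 0.234) = 19.2% at 4 weeks, 24.5% to 22.1% at 8, and 24.9% to 23.8% at 12.

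**5. Effect on start times.** Among observed starters the lag density is weighted by min(1, (g + 26 - t)/26). From a last entry on 31 December 2020, cuts on 31 January, 28 February and 31 March 2021 give g = 4.4, 8.4 and 12.9. The median is then too short by about 2-7 days, 0.4-4 days and under 2 days respectively.

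**6. Staggered sites.** Take six sites at assumed 18-day steps from 1 December 2019 to 29 February 2020, with section 5.0 volumes of 300, 75, 75, 75, 35 and 75 per six months. A 28 February 2021 cut leaves 4.8-12.7% of post-period starts unseen if Ottawa starts first and 12.8-24.9% if last. A 31 March cut leaves 1.3-5.8% and 4.0-13.1%.

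**7. A second lag model.** Log-normal, median 42 days, log-SD 0.4, 25% treated, no true effect, cut 28 February 2021. A site active 1 December 2019 shows 25.1% v 24.8% (odds ratio 0.99). A site active 29 February 2020 shows 25.0% v 18.8% (odds ratio 0.69), with medians of 42.0 v 39.9 days.

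**8. Primary endpoint.** With an assumed exponential order lag of mean m = 1 to 3 weeks, unseen = (m/26) × (exp(-g/m) - exp(-(g + 26)/m)). That is 0.1-3.0% at 4 weeks and under 1% at 8. For power, an odds ratio of 0.67 from 50% gives 40.1%; with 500 per period, power is 0.88, in line with section 5.0's claim of over 80%.

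**The case against.** The strongest reply is that sections 3.3 and 3.4 already settle the clock and section 6.0 is only a milestone list. That is right as far as it goes. A reader might infer from the single May 2020 date that February sites would get only 13-17 of 26 pre-period weeks and that the primary comparison would suffer. The documents do not support this, because the operative text gives each site its full periods. Even if the May date were imposed on every site, with even spacing and Ottawa last, about 428 of 635 pre-period patients would remain. Power at an odds ratio of 0.67 would be about 83% (428 v 428) or 86% (428 v 500), still above the plan's 80%.

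A second reply is that the plan never commits to one common cut. Section 3.4 says post-period collection mirrors the pre-period and that staff collect data throughout the study, which suggests rolling abstraction. If every chart were read at the same interval after the visit, the bias would not arise. This reply stands in part: the common cut is a possibility, not a stated plan. But no section sets such an interval.

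Third, there are safeguards. The planned regimen is recorded after the visit, clinic lists are daily or weekly, and section 4.0 promises caution on secondary endpoints. The planned regimen is less exposed to truncation. None of these recovers chemotherapy received or start dates that fall after the cut, and caution in interpretation does not remove a directional difference.

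Finally, every lag, the treated fraction, the site order and the cut date are assumed. That is fair: the direction is firm and the size is not.

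**Conclusion.** The point holds for the secondary endpoints and should be fixed. The date conflict is plain arithmetic for sites initiated after about early December 2019. The ascertainment gap depends on charts being read at a common cut, which the plan neither states nor excludes. In that case, and with mean lags of 6-10 weeks, about 9-23% of post-period chemotherapy starts are missed with 4 weeks after last entry, 2-12% with 8 and under 5% with 12. The timing shift is modest beside the effect on frequency. The bias largely fades once every site has about 12 weeks.

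A reader might conclude that the primary result or the sample size is unsound. Neither follows: order status is little affected if read about 4 weeks or more after last entry, and the stated power holds.

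**What to change.** Reconcile the section 6.0 dates with the per-site clock, and state a data-cut date.

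For chemotherapy received, treatment start times and chemotherapy cost only:

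- Use the same window from the first medical-oncology visit in both periods, with its length chosen and justified by the sponsor.
- Count only patients whose window has elapsed at the cut, and report the number pending by period rather than counting them as untreated.
- Compare start times among patients who started within the window, or use a censored time-to-start analysis among patients planned for chemotherapy (already collected under section 3.8). Report use separately as a proportion and read the two together, because PREDICT may change who is treated.
- Do not use a log-rank test on all patients as a timing test. In simulation with 30% v 22% use and identical start speed, it was significant 63-82% of the time.

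With an illustrative 12-week window and elapsed patients only, simulated false-positive rates were 3.9-5.6% for Wilcoxon and 5.0-5.8% for chi-square on use, against a nominal 5%.

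Leave the primary endpoint definition unchanged, apart from reading order status a few weeks after last entry.

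The cost is wording, plus either some late post-period patients left out of these endpoints or a later lock. With the staggered sites above, illustrative windows of 8, 12 and 16 weeks leave out about 6-17%, 14-30% and 28-45% of post-period patients at a 28 February 2021 cut. At 31 March the figures are 2-7%, 6-16% and 13-28%. Keeping every patient at a late-February site under a 12-week window would run to about 23 May 2021 (28 February + 84 days), after funding ends. No extra patients are needed.
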